8. PARTICIPANT IDENTIFICATION

8.1. Study Participants

Participants with a high risk of HCC will be included. Participants will have liver cirrhosis from ArLD, MASLD, chronic hepatitis C, chronic hepatitis B or genetic haemochromatosis, or with chronic liver disease and prior successful treatment for HCC without recurrence and who are back in surveillance with USS.

8.2. Inclusion Criteria

- Participant is willing and able to give informed consent for participation in the study AND
- All genders, aged 18 years or above AND
- Eligible for HCC US surveillance in the opinion of the local investigators AND
- Child Pugh score A or B AND
- Diagnosed with liver cirrhosis due to ArLD, MASLD, chronic hepatitis C, chronic hepatitis B, genetic haemochromatosis AND
- Have an annual risk of HCC of at least 3% as determined by the aMAP score (see 9.4 for details)
 OR
- Participants with chronic liver disease (with or without cirrhosis) who had successful treatment for HCC, have not had a recurrence and have returned to 6 monthly surveillance with USS

8.3. Exclusion Criteria

The participant may not enter the study if ANY of the following apply:

- Contraindication to MRI
- Known allergy / reaction to intravenous gadolinium contrast
- Prisoners
- Pregnancy or breast feeding
- Previous liver transplant
- Participants who are known to have indeterminate liver nodules on prior imaging requiring ongoing follow-up with MRI or CT
- Previous HCC treated with curative intent and still being followed up with CT or MRI with contrast for possible recurrence
- Estimated glomerular filtration rate of <30 ml/min/1.73m²

- Participant is on haemodialysis
- Participants who are unlikely to comply with the study procedures in the opinion of the local investigator
- In the view of the clinician, if the participant has a co-morbidity likely to lead to death within the following 12 months

9. PROTOCOL PROCEDURES

9.1. Recruitment

Recruitment centres will be secondary and tertiary care hospitals. Clinical and research teams within NHS Trusts will identify and approach potential participants and may send out the Participant Invitation Letter and Participant Information Sheet ahead of the research visit. A reply slip is included in the Participant Invitation Letter which potential participants can return to the recruiting site to express their interest in the study and be invited for a visit. Participants will be recruited if they fulfil the inclusion / exclusion criteria.

To facilitate recruitment to the study eligible participants may be identified from other cohorts of participants at risk of HCC, such as the Pearl study (IRAS 285362).

9.2. Participant identification from the Pearl study

The Pearl study is a prospective cohort study of people with cirrhosis in the UK, conducted by the same investigators as AMULET. The Pearl study investigators will identify, from the database, those participants who have indicated that they are happy to be approached to take part in future studies, their eligibility will be checked and those eligible will receive an Invitation Letter and Participant Information Sheet ahead of the research visit. If they are happy to take part they will ask to indicate it on the reply slip and return it back to the study team. The research team will contact and arrange a visit.

We will ask permission of Pearl study patients who are eligible and are recruited into AMULET to store their Pearl study number for the purposes of data linkage.

9.3. Screening and Eligibility Assessment

This section refers to the screening and eligibility checks for inclusion in the study (checking inclusion / exclusion criteria and determining the annual risk of HCC) and not to the screening / surveillance for HCC that may be happening as part of routine practice. The maximum duration allowed between screening and enrolment to the study will be 12 months. There will be no exceptions made regarding eligibility, i.e., that each participant must satisfy all the approved inclusion and exclusion criteria of the protocol. Screening will be done via review of the medical record and / or screening of the Pearl cohort as described above. During screening, available data in the medical record or in the Pearl and other databases will be used to check eligibility.

9.4. Determining the annual risk of HCC

Part of the screening procedures for eligibility will be the determination of the annual risk of HCC for each participant. A number of HCC risk scores have been described²⁸⁻³⁴ but most of them lack sufficient validation or are designed specifically for people with liver disease from a specific aetiology. The score that has been most extensively validated and the one that we will use to determine the risk of HCC or participants in our study is the "age, male, albumin-bilirubin, platelet count (aMAP)" score^{35, 36}. The score ranges from 0-100, where a score of <50 is associated with a low risk of HCC, a score of 50-60 is associated with an intermediate risk of HCC and a score >60 is associated with a high risk of HCC³⁵. Furthermore, the aMAP score can provide further information on the risk as a percentage risk of developing HCC over the next 3 years. For the purpose of our study high risk will be defined as an annual risk of HCC of at least 3% (or 3-year risk of HCC of at least 9%).

Our risk prediction strategy may be revised in the face of any future developments that refine and improve the aMAP score or its derivatives.

9.5. Informed Consent

The participant must personally sign and date the latest approved version of the Informed Consent form before any study specific procedures are performed.

Written and verbal versions of the Participant Information Sheet (PIS) and Informed Consent Form (ICF) will be presented to the participants detailing no less than: the exact nature of the study; what it will involve for the participant; the implications and constraints of the protocol; the known side effects and any risks involved in taking part. It will be clearly stated that the participant is free to withdraw from the study at any time for any reason without prejudice to future care, without affecting their legal rights, and with no obligation to give the reason for withdrawal.

The participant will be allowed as much time as wished to consider the information, and the opportunity to question the Investigator, their GP or other independent parties to decide whether they will participate in the study. Written Informed Consent will then be obtained by means of participant-dated signature and dated signature of the person who presented and obtained the Informed Consent. The person who obtained the consent must be suitably qualified and experienced and have been authorised to do so by the Chief/Principal Investigator. One copy of the signed Informed Consent will be given to the participant and another kept in their medical notes. The original signed form will be retained at the study site.

Continuous consent will be confirmed at subsequent visits.

9.6. Registration

This is a non-randomised study. Once participants sign the ICF they will be assigned a unique study identifier and will be registered on web-based registration systems (REDCap and XNAT).

9.7. Blinding and code-breaking

This is a single arm study evaluating nceMRI and USS as tests for HCC surveillance. The blinding procedures in the study will therefore focus on ensuring the acquisition and reporting of USS and nceMRI are blinded from each other.

Timing of USS and nceMRI acquisition and reporting

USS are usually performed and reported by the same operator. It is therefore usual practice for USS to be reported immediately after the acquisition of the data. On the other hand, nceMRI scans are usually acquired by MR radiographers and an MR radiologist reports on the data subsequently. There may therefore be an interval between acquisition and reporting of nceMRI data. For the purposes of this study, surveillance USS and nceMRI should preferably be acquired on the same day. Reports for both tests should be available to the clinical team within 4 weeks of the first scan being acquired. Therefore, the second scan can be acquired up to 4 weeks after the first scan, but in this case, the second scan must be reported on the same day it is acquired.

Blinding procedure

In any surveillance round, the surveillance test that is acquired first, will be labelled with and reported under the AMULET study identifier. This will ensure that the report and images for the first surveillance test are kept separate from the electronic patient record and the radiology department PACS systems and will not be available to the radiologist reporting the scan being performed second at each 6 monthly surveillance episode. Once the second scan is reported then the images and report of the first test will be un-blinded and uploaded to the electronic patient record and PACS system.

- 1. First scan is performed either USS or nceMRI
 - a. Scan is labelled and reported using AMULET study ID only no personal identifiers should be included
 - b. Report proforma is completed and entered into study database
 - c. The report and images should not be uploaded to the electronic patient record or radiology department PACS system at this point
- 2. Second scan is performed within 28 days either USS or nceMRI (whichever was not performed as the first scan)
 - a. Patient identifiers may be used and report/images uploaded as normal
- 3. After reporting of the second scan is complete, the report/images from the first scan should be un-blinded and uploaded to the electronic patient record and PACS system.

If sites are not able to implement any of the above blinding procedures due to logistical reasons, then investigators reporting USS and nceMRI will have to confirm in their report that they did not access the reports or images of contemporaneous scans.

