7 3D R ₂ * mapping High resolution R ₂ * mapping with 12 echoes with longer echo times (1– 18 ms).	1 min (2 x 16 s BH)	R ₂ * hyperintense for iron sparing lesions.	"Field effects" in R_2^* map.
8 3D T_1 mapping Variable flip angle T_1 , plus B_1 and B_0 mapping.	4 min (6 x 15 s BH)	T ₁ mild-moderately hyperintense.	"Field effects" in T_1 map.

nceMRI: reporting for the imaging findings

nceMRI will be evaluated by board-certified abdominal radiologists at each site using a standardised proforma. On nceMRI, a suspicious nodule is defined as a solid newly appearing nodule ≥ 1 cm that is not definitely benign. Diffuse infiltrative lesions with or without suspected tumour in vein are also considered suspicious. Simple cysts, haemangiomas, and lesions previously diagnosed as benign lesions are not considered suspicious, irrespective of the size.

nceMRI: reporting for the quality of the scans

Automated quantitative quality assurance (QA) of nceMRI in terms of image signal-to-noise ratio (SNR) measures will be performed and these results will be stored on the XNAT platform that will be used for imaging data management. Furthermore, nceMRI scans will be reported locally using a standardised proforma that will be developed based on other multicentre studies that have investigated implementation of MRI (e.g. STREAMLINE-C³⁹ and STREAMLINE-L⁴⁰).

Contrast enhanced magnetic resonance imaging

In addition to the checks for the safety of having an MRI scan (which will be the same as for the nceMRI scan) there will be added check for the safety of receiving intravenous gadolinium contrast. Gadolinium contrast is contraindicated in people with eGFR <30 ml/min/1.73m². Estimated GFR will therefore be checked prior to inclusion in the study (see exclusion criteria) and before each ceMRI procedure. For the ceMRI an intravenous cannula will be inserted into the participants arm by a radiographer or other appropriately trained person. Scans will be acquired before and after the administration of an intravenous contrast agent. Scans will be reported by study radiologists at each site using a standardised proforma including LI-RADS classification.

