9.10. Subsequent Study Visits

At each subsequent visit, the patient's eligibility to the study will be checked and patients will undergo another formal safety assessment before undergoing MR examinations. Patients will have to attend their MRI having fasted for at least 4 hours.

Each follow up visit will ideally take place on a single day but may take place on two separate days, with the first imaging scan and data collection taking place up to 28 days prior to the second imaging scan (see also section 9.7).

Participants will attend follow-up every 180 days for five visits after baseline (total of six visits including baseline). At each subsequent visit, confirmation of continuous consent will be obtained from the participant and an eligibility check will be carried out to ensure that participants still fulfil the inclusion and exclusion criteria.

Study visits will last for 120 minutes and assessments/procedures are as follows:

- Collection of Demographics and Medical History (duration 10 minutes)
- Physical Examination (recording of height and weight) (duration 5 minutes)
- Completion of MRI safety check (5 minutes)
- Clinical care USS (20 Mins)
- nceMRI (20 minutes)
- Completion of EQ-5D-5L and HADS questionnaires at the beginning of each study visit (30 minutes)
- Acceptability of MRI and USS as surveillance test questionnaire (to be completed immediately after the relevant scan on visit 5 only, 30 minutes)

Visit 6, final study visit (120 minutes)

At visit 6, in addition to the other study procedures listed above, a contrast enhanced MRI will be performed on all participants.

Contrast enhanced MRI will also be performed at any visit if the surveillance USS or nceMRI show a suspicious nodule for HCC.

Timing between visits

The baseline visit (visit 1) will be designated as D0. If the study procedures take place on different days for the baseline visit then D0 will be the first day on which study procedures were carried out. Once the baseline visit is completed, dates will be assigned for subsequent visits (visit 2: D180, visit 3: D360; visit 4: D540 etc).

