11.2. Description of the Statistical Methods

Statistical analysis for Primary outcome measure

Measures of diagnostic performance will be determined per round of surveillance and over the 30 months of study participation.

Diagnostic performance per round of surveillance

At each round of surveillance, the following data will be calculated and compared between USS and nceMRI.

- 1. Number and proportions of positive surveillance USS and nceMRI see section 9 for definitions of positive tests
- Number and proportions of true positive (TP) and false positive (FP) USS and nceMRI. As each positive test will be followed by a full contrast enhanced MRI, TP and FP tests per round of surveillance will be calculated
- 3. Positive predictive value (PPV) of USS and nceMRI

Diagnostic performance for the overall study period of 30 months

For the purpose of this analysis, each USS and nceMRI scan for each participant completing the study will be assigned only one of the 4 possible diagnostic categories of: true positive (TP) or false positive (FP), true negative (TN) and false negative (FN). The sum of TP, FP, TN and FN in this analysis will therefore be equal to the total number of participants completing the study. TP and FP will be determined at each visit as described above. TN and FN will be determined at the end of the study when participants undergo the reference standard ceMRI as part of the study protocol. FN results will also include those cases that present with HCC during the study without a prior positive test (interval cancers) or cases where both USS and nceMRI are negative tests but a ceMRI scan is triggered by an AFP>20. Cases that are initially FP may subsequently change diagnostic category. For this analysis, the diagnostic category which is applicable at the end of the study will be used. For example, if a finding initially classed as an FP develops into an HCC that was correctly identified by the surveillance tests, then the diagnostic test will be counted as a TP for this analysis.

Sensitivity and specificity estimates will be calculated separately for nceMRI and USS and compared. Statistical significance of the observed differences in sensitivity/specificity will be evaluated using the McNemar's test of paired proportions, with a two-tailed P-value <0.05 used as the significance criteria.

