22. APPENDIX A: SCHEDULE OF STUDY PROCEDURES

Procedures	Visits								
	Visit timing -360 days to Day 0 Screening	Baseline Day 0 (+28) Visit 1	Day 180 ±30 days Visit 2	Day 360 ±30 days Visit 3	Day 540 ± 28 days Visit 4	Day 720 ± 30 days Visit 5	Day 900 ±30 days Visit 6		
								Informed consent/continuous consent	
Demographics		x							
Medical history		x	x	x	x	x	x		
Physical examination		x	x	x	х	x	x		
MRI Safety Checks		x	x	x	x	x	x		
Case notes review	x	x	x	x	х	x	x		
Eligibility assessment Inclusion / exclusion criteria aMAP score calculation	x								
Standard of care liver USS		x	x	x	x	x	x		
Liver nceMRI		x	x	x	x	x	x		
Contrast enhanced liver MRI		*	*	*	*	*	x		
HADS		x	x	x	х	x	x		
EQ-5D-5L		x	x	x	x	x	x		
Patient experience questionnaires		x				x			
Adverse event assessments		x	x	x	х	x	x		

* A contrast enhanced liver MRI scan is mandatory at visit 6 and must be performed at any of the study visit standard of care ultrasound scan or non-contrast enhanced MRI scan show possible hepatocellular cancer

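### Section 9.7 blinds USS and nceMRI from each other but not nceMRI from the reference ceMRI, which at visit 6 is scheduled whatever the surveillance results

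*Protocol*

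**What the plan says.** - **Scope of blinding (Protocol 9.7).** "The blinding procedures in the study will therefore focus on ensuring the acquisition and reporting of USS and nceMRI are blinded from each other". The surveillance scan acquired first is held under the study ID, outside PACS and the patient record, until the second has been reported. The second may carry identifiers and be filed normally. The ceMRI does not appear in the procedure.
- **Timing (9.7).** On nceMRI: "There may therefore be an interval between acquisition and reporting of nceMRI data". On the window: "Reports for both tests should be available to the clinical team within 4 weeks of the first scan being acquired". If the second scan is acquired on a later date, the rule is stricter: "but in this case, the second scan must be reported on the same day it is acquired". The preferred arrangement, both scans on one day, has no such rule.
- **Visit 6 (9.10).** "At visit 6, in addition to the other study procedures listed above, a contrast enhanced MRI will be performed on all participants". Appendix A agrees: "A contrast enhanced liver MRI scan is mandatory at visit 6". So does section 7.
- **Role of that scan (11.2).** "TN and FN will be determined at the end of the study when participants undergo the reference standard ceMRI as part of the study protocol".
- **Readers (9.8.2).** Abdominal radiologists at each site report the nceMRI. On the ceMRI: "Scans will be reported by study radiologists at each site using a standardised proforma including LI-RADS classification". No rule asks for different readers or sets a reading order.
- **Fallback (end of 9.7).** Sites that cannot implement the blinding must have their reporters declare that they did not look at contemporaneous scans. Sites that do implement it declare nothing.

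**The concern.** In rounds 1 to 5 the ceMRI follows a positive surveillance report or an AFP trigger, so the index reads are normally complete before the reference exists. At visit 6 that protection goes, because the ceMRI is booked regardless. If a radiologist can see the ceMRI when reporting the nceMRI, the index test is no longer independent of the reference standard.

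The exposure is unequal. Section 9.7 notes that USS is usually reported straight away by its operator, whereas nceMRI is read later by someone else. Knowledge of the ceMRI could lead a reader to call a lesion that would otherwise have been missed (FN to TP), or to dismiss an equivocal nodule when the ceMRI is clean (FP to TN). Both shifts favour nceMRI in the paired McNemar comparison of sensitivity and specificity.

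**Working it through.** **1. When can the ceMRI be seen before the nceMRI report is complete?** Taking the visit 6 arrangements allowed by 9.7 in turn:

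| nceMRI position | What 9.7 provides | Remaining exposure to ceMRI |
|---|---|---|
| First | Study ID only, kept out of PACS; proforma listed before the second scan | Reduced: linking to the patient's other images is harder, but ceMRI is not barred |
| Second, later day | Report due on the day of acquisition | Reduced: short interval, no reading order |
| Second, same day as USS | Identifiers allowed, normal filing, no same-day rule, reports due within 4 weeks | Clearest: ceMRI may be on PACS when the nceMRI is read |

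The protocol does not say whether the visit 6 nceMRI and ceMRI are acquired in one session or two.

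**2. What does a changed call do to the 2×2 table?**

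- *LI-RADS 5, or HCC confirmed by the MDT or biopsy.* An nceMRI FN becomes a TP.
- *LI-RADS 4, unresolved.* With no positive test, 9.8.1 classes LI-RADS 4 on the end-of-study scan as HCC, so nceMRI is an FN. If the nceMRI is called positive, the ceMRI becomes one that follows a positive test. LI-RADS 4 is then indeterminate, follow-up stops when visit 6 was due, and the lesion is classed as negative. The nceMRI is an FP, which agrees with the Figure 1 footnote in section 7. This is not an FN-to-TP conversion.
- *Equivocal nodule, clean ceMRI.* A dismissed nodule turns an FP into a TN.

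**3. Size per case.** Section 11.3 plans on 50 HCCs and 200 controls.

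- Sensitivity: 1/50 = 2 points per FN converted to TP.
- Specificity: 1/200 = 0.5 points per FP converted to TN.
- Assumed range of 1 to 5 converted HCCs: 1/50 = 2 points to 5/50 = 10 points. The sensitivity differences in Table 2 run from 70 − 50 = 20 to 90 − 30 = 60 points.

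**4. Effect on the test, for scale only.** Table 2 is first reproduced with

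n = (1.96√p_d + 1.2816√(p_d − d²))² / d²,

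where d is the difference and p_d the discordant proportion. A within-patient correlation of 0.1 is assumed because it reproduces the printed sensitivity figures.

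- 80% v 50%: p_d = 0.50 − 2 × 0.1 × √(0.8 × 0.2 × 0.5 × 0.5) = 0.46, d = 0.30, n = 49.4, rounded up to 50 (Table 2: 50).
- 70% v 50%: p_d = 0.50 − 2 × 0.1 × √(0.7 × 0.3 × 0.5 × 0.5) = 0.454, d = 0.20, n = 115.1, rounded up to 116 (Table 2: 116).

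Power with 50 HCCs is Φ[(d√50 − 1.96√p_d)/√(p_d − d²)].

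- True 70% v 50%: Φ[(1.414 − 1.321)/0.644] = 56%.
- Five conversions, with the resulting 80% v 50% treated as an ordinary pair (p_d = 0.46): Φ[(2.121 − 1.329)/0.608] = 90%.
- Five conversions, all missed by USS as well, so that p_d rises by 5/50 to 0.554: Φ[(2.121 − 1.459)/0.681] = 83%.

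With zero correlation, the first two figures are 52% and 87%. In this scenario, five cases would raise the chance of a significant result from just over half to between 83% and 90%.

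**The case against.** The strongest reply is that the protocol already implies the right order. Section 9.8.1 gives the end-of-study ceMRI to people who have completed all six rounds without a positive test. Its two LI-RADS rules cannot be applied to a visit 6 scan unless the round 6 result is known. This stands as an implied order of events, but it sets no order of reading: the result could be entered after the ceMRI has been seen and the rule chosen then.

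The study-ID hold and the same-day reporting rule do narrow the exposure, as the table shows. They do not close it. The fallback declaration is broad enough to include a ceMRI, but it binds only sites that cannot follow the main procedure.

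A reader might infer more than the documents support:

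- *That every participant is exposed.* Participants with HCC or a transplant have no further visits (9.11), and those with LI-RADS 3 or 4 lesions under interval imaging are suspended (9.8.1). Section 9.8.1 also describes a narrower group for the end-of-study scan than section 9.10 and Appendix A.
- *That every unblinded call turns an FN into a TP.* Unresolved LI-RADS 4 lesions become FPs.
- *That 10 to 20 points of sensitivity are at risk, or that visit 6 supplies most FNs.* Nothing in the protocol says how many HCCs will first appear on the visit 6 ceMRI. At 90% nceMRI sensitivity there are only 50 × 0.10 = 5 FNs in all, so a 20-point shift is impossible. FNs also include interval cancers and AFP-triggered diagnoses (11.2).

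**Conclusion.** The gap is real but narrower than it first appears. Section 9.7 does not name the ceMRI, and no passage requires the visit 6 nceMRI report to be complete before the ceMRI is read. A compliant site could therefore read the index test with the reference available. The probable direction favours nceMRI, partly offset where a LI-RADS 4 lesion stays unresolved.

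The firm figure is 2 points of nceMRI sensitivity per converted case with 50 HCCs. The range of 2 to 10 points rests on an assumed 1 to 5 cases and is not a prediction of bias. The power figures rest further on a true 70% v 50% and a correlation of 0.1. Even if few reads were affected, the study could not show afterwards that its visit 6 reads were independent of the reference. This is a cheap improvement to the procedure; it does not invalidate the design.

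**What to change.** Add to section 9.7:

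1. At visit 6, the USS and nceMRI proformas are completed and locked with a time stamp in REDCap before the ceMRI images or report are opened.
2. Until then the ceMRI is held under the study ID, as is already done for the first surveillance scan.
3. The final report states how many visit 6 USS and nceMRI reads were locked before the ceMRI was opened.

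Separately, reconcile section 9.8.1 with sections 7 and 9.10 and Appendix A on who has the end-of-study ceMRI.

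The cost is procedure wording and a database lock, with no extra scan or reader. The downside is a short delay to the ceMRI report when the nceMRI is not read the same day. The change has to be in force before visit 6 scans begin. From the planned recruitment start of 1 November 2024, Day 900 falls on 20 April 2027, or somewhat earlier where a participant's schedule resets. A read made with the ceMRI in view can be repaired later only by re-reading.

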7. STUDY DESIGN

This will be a single-arm, multi-centre, prospective cohort study evaluating the diagnostic accuracy of nceMRI and USS for diagnosis of HCC in people at high risk of HCC. People at high risk of HCC include those with liver cirrhosis and a high risk of HCC, or those with previous successfully treated HCC who are back in surveillance with USS. Participants will be recruited from UK hospital-based liver clinics over a period of 18 months and study procedures will take place in UK hospitals and academic centres. Participants will undergo 6 rounds of 6 monthly surveillance with nceMRI and USS over 30 months. Participants will be invited to complete questionnaires at each study visit. Relevant data will also be extracted from the participants' medical records. If at any surveillance round, a surveillance test raises a concern for the presence of HCC, participants will undergo full diagnostic contrast enhanced MRI (ceMRI) to determine whether HCC is present or not. In cases where indeterminate lesions for HCC are reported, these may require further tests including contrast CT, follow-up contrast enhanced MRI, or biopsy as directed by the clinical team. All participants will undergo diagnostic full contrast enhanced MRI at the end of their study participation. If an HCC is diagnosed at any point in the study, then participants will receive treatment according to standard clinical protocols as part of standard of care.

Long-term follow up of medical records from NHS England, the NHS Central Register for Scotland and other patient registries may be conducted for up to 10 years after the end of the active follow up phase. Data obtained from these registries will include but is not limited to liver disease, decompensation episodes, HCC diagnosis, liver transplantation and death. There will be no additional involvement from study sites or participants, as the long-term follow up only involves accessing centrally held medical data.

The overall study design and participant flow is summarised in Figure 1.

Figure 1: AMULET study design and patient flow

Abbreviations: HCC: hepatocellular cancer; USS: ultrasound scan; nceMRI: non-contrast enhanced MRI; AFP: alpha-fetoprotein; HADS: hospital anxiety and depression scale; +ve: positive; -ve: negative [#] see section 9.4 for the description of the procedure for HCC risk estimation

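### Blinding between USS and nceMRI covers only the current round; no rule limits a study reader's access to the other modality's earlier-round results at visits 2 to 6

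*Protocol*

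**What the plan says.** Section 9.7 gives the purpose of blinding as "ensuring the acquisition and reporting of USS and nceMRI are blinded from each other", with no limit to a single round.

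The procedure is narrower. The first scan of a round is held under the study identifier so that it "will not be available to the radiologist reporting the scan being performed second at each 6 monthly surveillance episode". The hold then ends: "Once the second scan is reported then the images and report of the first test will be un-blinded and uploaded". The destination is PACS and the participant's electronic record. For the second scan, "Patient identifiers may be used and report/images uploaded as normal". Sites that cannot follow the procedure rely on a declaration: readers "will have to confirm in their report that they did not access the reports or images of contemporaneous scans".

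Section 7 sets the repetition: "Participants will undergo 6 rounds of 6 monthly surveillance with nceMRI and USS over 30 months". Section 11.2 sets the use of the results: "Sensitivity and specificity estimates will be calculated separately for nceMRI and USS and compared", by McNemar's test, with one category per test per participant over the 30 months.

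**The concern.** The aim and the procedure do not match. Once a round closes, both modalities' images and reports are on the record. At the next round the USS operator may look at earlier nceMRI, and the nceMRI radiologist at earlier USS, before assigning the study category. No section of the protocol forbids this or asks for it to be recorded.

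The comparison is between two surveillance tests assessed separately. If what one test showed at a previous round tells the other's reader where to look, or what to dismiss, the later read is partly a combined read. The pooled 30-month estimates would then mix unaided and aided reads, and nothing the protocol asks for would allow them to be separated.

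**Working it through.** **1. Scope of the blinding, by round.** Six rounds, less the baseline round, leaves 6 − 1 = 5 rounds (visits 2 to 6) that can follow release of both tests. This counts rounds, not reads actually affected.

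| Reader could see | Covered by the 9.7 procedure? | Covered by the fallback declaration? |
|---|---|---|
| Other modality, same round | Yes, all six rounds | Yes |
| Other modality, earlier rounds | No | No |

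**2. Routes by which a previous round's result can reach a later read.**
- *Subthreshold findings.* Section 9.8.2 classes US2 as negative and returns the participant to surveillance. An nceMRI nodule under 1 cm is likewise not suspicious. If it grows, the other modality's reader may already know its site.
- *Cleared lesions.* Under section 9.8.1, participants whose lesions are found negative re-enter surveillance. A reader who knows of the clearance is less likely to call the lesion again, which bears on specificity.
- *History-dependent definitions.* In section 9.8.2 an nceMRI nodule must be new to be suspicious, and lesions already diagnosed as benign do not count. Neither condition is tied to earlier nceMRI.
- *Reclassification.* Section 11.2 lets an earlier false positive become a true positive if it develops into an HCC that the tests identify.

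**3. What limits the routes.** Under section 9.8.1, participants with HCC have no further surveillance, and those with LI-RADS 3 or 4 lesions under interval contrast imaging are suspended. A cancer confirmed after one test's positive result therefore cannot be credited to the other test at a later round.

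**4. Does the direction follow?** The protocol gives no carry-over rate, so this is an illustration on assumed values. Start from Table 2 (section 11.3): sensitivities of 80% and 50%, 90% power, two-sided 5%, stated requirement 50 HCCs. Let p10 be the proportion of HCCs found by nceMRI alone, p01 the proportion found by USS alone, s = p10 + p01 and d = p10 − p01.

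n = (1.96√s + 1.2816√(s − d²))² / d²

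Independent tests give 55. A between-test correlation of 0.1 (inferred, not stated in the protocol) gives
- p10 = 0.80 × 0.50 − 0.1 × √(0.8 × 0.2 × 0.5 × 0.5) = 0.40 − 0.02 = 0.38
- p01 = 0.50 × 0.20 − 0.02 = 0.08
- s = 0.46, d = 0.30, n = 49.4, rounded up to 50, as stated.

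The same correlation reproduces 15 of the 16 numeric cells of Table 2.

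Now let c be the share of cancers found by one test alone that the other is also credited with through knowledge of a previous round's result. They move from found by one test to found by both: p10 becomes 0.38(1 − c) if USS gains, and p01 becomes 0.08(1 − c) if nceMRI gains. With 50 HCCs, power = Φ[(d√50 − 1.96√s) / √(s − d²)].

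| Who gains | Difference at c = 10%, 20%, 30% (points) | Power at c = 10% to 30% |
|---|---|---|
| Neither (c = 0) | 30 | 90% |
| Both | 27, 24, 21 | 87% to 76% |
| USS only | 26.2, 22.4, 18.6 | 84% to 61% |
| nceMRI only | 30.8, 31.6, 32.4 | 92% to 96% |

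The sign of the effect depends on who gains, and the documents do not settle that. At c = 10% to 30%, USS would be credited with 0.38 × 50 × c = 1.9 to 5.7 extra cancers. Given step 3, nothing in the protocol shows that so many are plausible.

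**The case against.** The best defence is that same-round blinding is sound and applies at every round, that filing results serves care, and that the main carry-over route is closed because diagnosed cancers leave the study. Known indeterminate nodules needing CT or MRI follow-up are excluded at entry (section 8.3), and section 9.8.2 cites data that subthreshold USS lesions seldom progress. First scans are also read under the study identifier alone, which discourages looking up the record, though it does not forbid it. All of this limits the size of the problem; none of it supplies a rule on earlier rounds.

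A reader might infer three stronger things that the documents do not support:
- *Blinding holds only at baseline.* It does not fail later: the two scans of each round are kept apart at all six rounds.
- *Stand-alone performance is not measured.* Baseline is free of study carry-over. Access at later visits is permitted, not required, so contamination is possible rather than established.
- *USS will be flattered and power lost.* That assumes a one-way gain to USS for which the protocol gives no figure. A gain to nceMRI alone raises the difference and the power.

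**Conclusion.** The gap is real and plain in the text: section 9.7 states an unrestricted aim, and its procedure and declaration protect only the current round. At visits 2 to 6 a study reader may use the other modality's earlier results, and nothing asks for that to be recorded. The consequence is a possible bias in the 30-month paired sensitivity and specificity, of unknown size and direction, confined to the routes in step 2 of the working. The figures in step 4 rest on an inferred correlation of 0.1 and an assumed c; they show that the direction is open and do not predict an effect. The point does not invalidate the design, but it is worth correcting because the correction is cheap and unrecorded access could not be adjusted for later.

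**What to change.** In section 9.7:
1. Require the study category (US1, US2 or US3 for USS; suspicious nodule yes or no for nceMRI) to be entered on the proforma before the reader opens the other modality's surveillance images or reports from any round.
2. Keep earlier scans of the same modality, and lesions already confirmed benign on ceMRI or histology, available to both readers, since the nceMRI definition needs that history.
3. Extend the fallback declaration to contemporaneous or earlier scans of the other surveillance modality.
4. Record any such access on the proforma, so that a sensitivity analysis can leave those reads out.

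Release to the patient record and the clinical team is unchanged, and the full record is open once the category is entered.

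The cost is a protocol paragraph, a proforma item and brief reader training, with no extra scans or readers. The drawbacks are a two-step read, possibly more time for the USS operator, who usually scans and reports in one sitting, and reliance on reader declaration at sites that cannot hide PACS. Some carry-over remains by design, because both readers will know which lesions have been confirmed benign.
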